Brief Description of Study Procedures	
This is a parallel randomized controlled trial. Eligible patients who consent will be randomized to one of two groups: (1) the intervention group who will be given a Dexcom G6 for CGM, or (2) the control group who will follow their current standard finger-prick protocol via a provided Contour Next ONE glucometer. The CGM group must download the Dexcom G6 and Clarity mobile apps for data capture, whereas the standard of care group will use the Contour Next mobile app for their respective readings.
 
The Dexcom G6 captures real-time, dynamic glucose data every five minutes. Devices used in this study are FDA approved and commercially available.

Primary Endpoint	Hemoglobin A1c (HbA1c) level
Secondary Endpoints	Glycemic variability per mean amplitude of glycemic excursion (MAGE), coefficient of variation of HbA1c, range of HbA1c, frequency of hypoglycemic events, healthcare utilization per count of inpatient/outpatient visits, cost of care, current HEDIS performance on diabetes and behavioral health measures, coding specificity for diabetes, emergency department visit per 1000 rate, overall and for patients with diabetes, and hospitalization per 1000 rate related to
	diabetes, and self-reported behavioral changes (e.g. feeling more empowered to self-manage care, engaged with changing healthcare behaviors, and patient perceptions of the technology).
Analysis Population(s)	Patients with diabetes treated at all Reimagine Primary Care facilities (Avenues Internal Medicine, Cottonwood Family Medicine, Cottonwood Senior Clinic, and Holladay Internal Medicine) from 1 November 2018 to 31 December 2019 will be included in this study.
Benefits	Successful demonstration of CGM will allow patients to manage their condition, which may avoid the highs and lows of glucose monitoring and make patients feel better. This may reduce healthcare utilization and cost for the patients and the healthcare system as a whole. Furthermore, general knowledge on how to engage with patients in remote monitoring pilots will be better understood through this study.
Risks	This study includes recruiting patients and data will be collected. To minimize any breach in of private information the team will store data within the enterprise data warehouse/medical record, REDCap, and on secured mobile applications from Contour Next and Dexcom. While all devices used are FDA approved, there could be challenges for new users when using the new Dexcom G6

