- **Process for Aim 1e:** Measure the patient-level change in rate of hypoglycemic events as the patient-level slope of the six-month linear change in the so-called “intensity” (λ) of the estimated nonhomogeneous Poisson point process. Once we’ve computed each patient’s six-month linear change in λ , we will compare the distributions between randomized groups. Note that the motivation for measuring change in frequency as the slope of λ estimated from a non-homogeneous Poisson process is that it allows us to compare changes in frequency of hypoglycemic events between groups with different modes of monitoring (continuous vs daily).

Aim 2: Assess impact of CGM on healthcare utilization and cost

Specific Aim 2a: Measure the effect of CGM vs. standard finger-prick protocol on healthcare utilization

- **Hypothesis for Aim 2a:** The count of primary care, specialist, and emergency department visits or hospital stays over six months will be fewer among those randomized to CGM than that among those randomized to standard finger-prick protocol.
- **Process for Aim 2a:** For each patient, count their visits to a primary care provider or specialist or emergency department/hospital admission. Next, compare the distributions of visit counts between randomized groups using a Poisson test, aggregated as well as stratified by visit type. Other metrics for evaluating utilization may include: current HEDIS performance on diabetes and behavioral health measures, coding specificity for diabetes, emergency department visit per 1000 rate, overall and for patients with diabetes, and hospitalization per 1000 rate related to diabetes.

Specific Aim 2b: Measure the effect of CGM vs standard finger-prick protocol on cost

- **Hypothesis for Aim 2b:** The total variable cost associated with healthcare services/visits over six months will be fewer among those randomized to CGM than that among those randomized to standard fingerprick protocol.
- **Process for Aim 2b:** For each patient, measure total variable cost of associated healthcare services and visits. Then compare the distribution of costs between randomized groups using the Wilcoxon rank-sum test, a non-parametric analogue of Student’s *t*-test.

Aim 3: Qualitatively understand patient perspective of CGM

Specific Aim 3a: Record patients’ self-reported willingness to participate in a CGM pilot

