3.0 STUDY DESIGN

This is a pilot, parallel randomized controlled trial of CGM versus a standard finger-prick protocol among patients with type I and II diabetes treated at Intermountain Healthcare’s Reimagine Primary Care Clinics. Patients will

be eligible if their most recent HbA1c level is $\geq 6.5\%$ and they are either currently using a glucose meter or are prescribed a glucose meter at their index encounter. Upon consent, which will occur within in a private office/room within the Reimagine Care Clinic, patients will be randomized into one of two groups:

- **Intervention group:** CGM using a Dexcom G6 to measure glycosylated hemoglobin levels every five minutes. Patients will be asked to download the Dexcom G6 and Clarity applications (to have access to their real-time data) and be given a link to complete an exit survey in REDCap near the end of their study participation. Data will be sent via Bluetooth and then exported by the Intermountain research team into a Tableau (or similar) dashboard for data analysis/comparison (**Appendix A**)
- **Control group:** A standard finger-prick protocol that will require patients to continue with their daily fingerprick regimen established by their physician. This group will be given a Contour Next One meter to ensure that each patient is receiving the same level of accuracy by the same device. A review by Ekhlaspour et al of 17 glucose meters demonstrated wide variability, with only two devices achieving the 2013 ISO standard (with the most accurate being the Contour Next) [7]. Patients in the control group will be asked to download the Contour Next application which will send data via Bluetooth similar to above. Data will be aggregated, and protected health information removed prior to analysis (by Intermountain Healthcare and Savvysherpa). At the end of the study, patients will be asked to complete a short survey in REDCap about their willingness to participate in future studies (**Appendix A**).

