Randomization will be assigned *a priori* using a random number generator from Microsoft Excel. Sub-Investigator will then transcribe these numbers and order them individually in concealed envelopes and present them to the Research Coordinators to ensure the CRC is blinded. At time of consent the Research Coordinator will hand the patient the earliest numbered envelope to randomize. . Patients in both randomized groups will be given the devices and one month supplies to ensure compliance with the protocol. The Study Coordinator and patient will exchange contact information so that the CRC may resupply the patient with necessary equipment at the end of their month supply. The CRC may meet the patient at their Reimagine Care Clinic or off site for patient convenience. All patients are expected to participate for six months, which is near the minimum duration sufficient to measure clinically meaningful changes in hemoglobin A1c related to gradual behavioral changes (e.g., diet, exercise, insulin administration). Further, each patient will complete 2 mandatory blood draws and one elective blood draw at their designated Reimagine Care Clinic to evaluate HbA1c level changes over the course of the study. Baseline HbA1c must be completed on day of enrollment (± 2 days) which Intermountain Healthcare may choose to cover if not paid for by patient's SOC. An elective blood draw will be considered for data if completed at 3 months (± 1 week) and a third required blood draw upon study completion (± 2 weeks) which the study may also choose to cover if not SOC. 2 weeks from 180 enrollment) which the study may pay for if not covered by patient's SOC. We postulate that those that have a more consistent interstitial glucose profile (which avoid the high peak to valley swings), will have a more pronounced difference in pre and post HbA1c levels. Specific Aim #1 above will help our team understand the relationship between interstitial glucose and HbA1c, along with other outcomes of interest which include weight loss, alterations in diet, change in physical activity, etc.

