4.2 Methods

Patients will be screened for eligibility per Inclusion and Exclusion criteria (See Sections 3.3.1 and 3.3.2 respectively) and consented as described in Section 4.1.

The following information will be obtained from each subject's medical records, and/or during procedures, treatments, study-specific visits, and/or follow-up visits that are generally part of their usual or specialized care:

- Patient's ID number (EMPI)
- General demographic information (age, gender, height, weight, race, ethnicity)
- Patient's contact information (email, home address, and phone)
- Health history (personal health history, previous laboratory and glucose test results, medications, healthcare utilization and cost data)
- Current medications/medication history
- Glucose levels and historical A1c reports

Group #2 data will be transmitted from the Contour Next One device to the Contour mobile app via Bluetooth. Should this process fail, a contingency plan has been devised for patients to manually record their readings in an online REDCap form or provide their readings to their Research Coordinator who will properly store the data. Patients in the intervention group will have their data automatically uploaded via the Dexcom G6 app where it will then be obtained by Intermountain Healthcare researchers. No protected health information will be shared with those outside of this research study unless approved by the IRB. Coordinators will check in with the patients on a monthly basis (or more frequently for non-compliance) to ensure proper data entry and to answer any questions (if necessary).

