12.0 APPENDIX A

This section provides the questions which will be entered into REDCap and patients asked to complete at the end of the CGM study. There will be branching logic used based on the specific group assigned.

- 1. Which group were you assigned to?**
 - a. Group 1 (Dexcom G6)
 - b. Group 2 (ContourNext One)
- 2. What was the main reason that you signed up for this trial? _____.**
- 3. What was your biggest concern when you considered participating in this trial? _____.**
- 4. Were you initially disappointed with your group assignment?**
 - a. Yes
 - b. No

4b. Why were you disappointed with your group assignment? _____.
- 5. (For Group 1 participants): Did the Dexcom G6 impact your glucose management? For example, did it change your diet?**
 - a. Yes
 - b. No
- 6. (For Group 1 participants): Did the Dexcom G6 impact your glucose management? For example, did it change your exercise regimen?**
 - a. Yes
 - b. No
- 7. How did Dexcom G6 impact your glucose management? _____.**
- 8. (For Group 1 and 2 participants): On a scale of 1-5, where 1 is not helpful and 5 is extremely helpful, how would you rate the device?**
- 9. (For Group 1 and 2 participants): On a scale of 1-5, where 1 is extremely poor and 5 is extremely healthy, how would you rate your health BEFORE starting this study?**
- 10. (For Group 1 and 2 participants): On a scale of 1-5, where 1 is extremely poor and 5 was extremely healthy, how would you rate your health AFTER starting this study was completed?**
- 11. (For Group 2 participants): Did the ContourNext One impact your glucose management? For example, did it change your diet?**
- 12. (For Group 2 participants): Did the ContourNext One impact your glucose management? For example, did it change your exercise regimen?**
- 13. How did the ContourNext One impact your glucose management? _____.**
- 14. Did your glucose levels decrease between the initial enrollment and the end of the study? (Suggest inserting this filter question.)**
 - a. They increased
 - b. The decreased

c. No change

15. Would you be willing to participate in future Intermountain pilots in your primary care clinic? a.

Yes

b. No

16. General Comments. In the space provided, please feel free to add any other comments regarding your participation in this study. _____.

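### Self-reported change has no prospective baseline and rests on recall by patients who know their arm, and follow-up weight has no stated time point or window

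*Combined protocol and SAP*

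**What the plan says.** **Outcomes.** The secondary endpoints in the synopsis end with "self-reported behavioral changes (e.g. feeling more empowered to self-manage care, engaged with changing healthcare behaviors, and patient perceptions of the technology". Section 3.0 (Study Design) also names "other outcomes of interest which include weight loss, alterations in diet, change in physical activity, etc".

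**Survey timing.** The only instrument is the Appendix A survey. Its opening lines have "patients asked to complete at the end of the CGM study". Section 3.0 has the CGM group "complete an exit survey in REDCap near the end of their study participation", and Section 3.3 gives the end-of-study survey to both groups. No section describes a questionnaire at enrolment.

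**Survey content.** Item 9 asks, on a 1-5 scale, "how would you rate your health BEFORE starting this study". Item 10, directly after it, asks the same about health after the study. Items 5-6 (CGM) and 11-12 (control) ask whether the device affected glucose management, with a change in diet or in exercise as the example.

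**Weight.** Section 4.2 lists weight once, among the demographic items. The sources for that list are medical records, procedures, treatments, study-specific visits and "follow-up visits that are generally part of their usual or specialized care". No date or window is attached. The completion criteria in Section 5.1 cover the intervention course, the study procedures, the two required draws and the exit survey, and do not mention weight.

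**The concern.** A change needs a value from before and a value from after. Here the before value is either supplied from memory six months later or not asked for at all.

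The patient giving that answer has used a known device throughout. By item 9, the same survey has already asked for the assigned group (item 1), any disappointment with it (item 4) and how helpful the device was (item 8). Recalled health can then differ between arms because of how patients feel about their device, even if true change does not.

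The diet and exercise items ask patients to attribute a change to the device and do not measure a level of either. The question also means different things in the two arms. CGM patients are asked about a new technology. Controls continue their existing finger-prick regimen and may already have used a meter, so a control patient who changed diet for other reasons could properly answer no.

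For weight, a follow-up value taken only when a patient happens to attend would depend on attendance. Aim 2a expects attendance to differ by arm: "The count of primary care, specialist, and emergency department visits or hospital stays over six months will be fewer among those randomized to CGM".

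These data are meant to be used. Section 1.1 calls understanding the effect of real-time knowledge on behaviour critical before more sites are added, and Aim 3c lets survey results inform changes to clinical operations. A baseline that was not collected cannot be recovered in the analysis.

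**Working it through.** **1. The plan's own figure.** Section 7.2: 125 × (1 − 0.20) = 100 analysed, or 50 per arm if allocation is 1:1 (assumed). Its example gives d = 1/1.25 = 0.8. With a two-sided alpha of 0.05 (assumed; alpha is not stated), the standard error in SD units is √(2/50) = 0.20, and power = Φ(0.8/0.20 − 1.96) = Φ(2.04) = 97.9%. The statement of more than 80% power for HbA1c holds, and nothing below alters it.

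**2. What is collected, and when.**

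| Outcome | Before | After |
|---|---|---|
| Self-rated health | Recalled at exit (item 9) | Current rating at exit (item 10) |
| Diet, exercise | No level asked | No level asked; attribution to device only |
| Empowerment, engagement | Not asked | No direct item in Appendix A |
| Weight | Obtainable at enrolment or from records; no time stated | Possible under Section 4.2; no time or window stated |
| HbA1c | Enrolment ± 2 days | About day 180 ± 2 weeks |

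Only HbA1c has a scheduled value at both ends.

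**3. Are patients aware of their arm?** Yes. The devices differ visibly, and items 1 and 4 ask about the assignment. The blinding of the coordinator in Section 3.0 refers to envelope concealment before assignment and does not bear on the patients' answers.

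**4. Illustration for recall.** Assume 50 per arm, no true effect, a two-sided 5% comparison of item 10 minus item 9, and a shift b between arms in recalled health, in SD units of that difference. The false-positive rate is Φ(b/0.20 − 1.96) + Φ(−b/0.20 − 1.96).

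| b (SD) | False-positive rate |
|---|---|
| 0 | 5.0% |
| 0.1 | 7.9% |
| 0.2 | 17.0% |
| 0.3 | 32.3% |
| 0.4 | about 52% |
| 0.5 | 70.5% |

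The documents give no value for b and plan no such comparison.

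**5. Illustration for weight.** Assume that weights arise only at usual visits, that visits occur at random at a mean interval of m days, and that the window is day 180 ± 2 weeks, which is 14 + 1 + 14 = 29 days. The share with a weight in the window is 1 − exp(−29/m). With 20% fewer visits it is 1 − exp(−0.8 × 29/m).

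- m = 90: 27.5%, and 22.7% with fewer visits.
- m = 180 (one visit in the six months): 14.9%, and 12.1% with fewer visits.
- If weight is in practice taken at the final draw, nearly every completer has one and these figures do not apply.

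Neither the visit interval nor the 20% reduction comes from the documents.

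**The case against.** The strongest reply is that these outcomes are peripheral and the analysis is descriptive. Self-rated health is not a listed endpoint, appears in no aim and is absent from Section 7. Aim 3 is headed as qualitative, Aim 3b targets CGM patients only, and Aim 3c says to summarise. Weight, diet and activity appear once, with no hypothesis or test. The trial is described as a pilot. Perceptions of a new device, satisfaction with it, and having felt empowered by it are properly asked afterwards and have no baseline. All of this stands. It limits the weight of the point, and it means that a baseline form covering only health, diet and activity would leave the listed endpoint untouched.

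A reader might infer that these outcomes have no usable baseline or follow-up value at all. The documents do not support that. Item 10 is a genuine end-of-study rating. Section 4.2 includes study-specific visits among its sources, so weight is not confined to usual care. Patients are in the clinic at consent and at the final draw, so a weight could be taken at either.

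The reply does not remove the gap. The synopsis lists behavioural change, not only perceptions, as an endpoint, and Section 3.0 speaks of weight loss and of changes in diet and activity. Nothing in the plan secures a prospective before value for the self-reported items or a dated follow-up weight.

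**Conclusion.** The point holds in a limited form. Self-reported change has no prospective baseline: recalled health comes from patients who know their arm, and diet and exercise are recorded as attribution to the device. Follow-up weight has no stated time point or window, so it may be available only opportunistically, and availability could differ by arm if visit rates do.

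The size of any bias cannot be taken from the documents. It would be wrong to read the roughly 52% at a 0.4 SD shift as a false-positive rate of this trial, or the 12% to 28% as its expected availability of weights. The first describes a comparison that the plan does not make. The second assumes a visit rate, and a restriction to usual-care visits, that the plan does not state. Both show only the direction of the problem and how it would scale.

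The primary HbA1c analysis and the sample size are unaffected. This is a worthwhile low-cost improvement to secondary and exploratory data.

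**What to change.** 1. At REDCap consent, before the envelope is opened, add a short form with present-tense 5-point items on current health, diet, physical activity, and confidence or engagement in self-management. The last is needed so that the listed behavioural endpoint is covered.
2. Repeat the same items in the exit survey in both arms, in place of the recalled item 9.
3. Record weight in both arms at the two mandatory clinic blood draws, under the draw windows already set.
4. Keep satisfaction and perceptions of the device as exit-only items.

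If no baseline form is added, state in the plan that the before-after items will be reported only as descriptive retrospective perceptions.

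The cost is a handful of survey items in a system already open at consent, and one scale reading at each of two visits that already take place: a minute or two at enrolment and again at the final visit. The form would also give baseline data on the 20% of patients expected to be lost, who may otherwise provide no survey data.
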